3. RATIONALE

To better enhance the care of patients with an acute exacerbation of COPD, Carolinas HealthCare System (CHS) has designed a COPD clinical pathway, a structured multidisciplinary care plan. The care plan utilizes a data system that identifies patients with exacerbation and care gaps in real-time. It includes an EMR based order set, patient education, and discharge criteria. A COPD pathway coordinator who works to close care gaps and ensure a standardized approach is also part of the care plan.

At participating CHS hospital, patients who are admitted with a suspected acute COPD exacerbation, will enter the COPD clinical pathway. The COPD clinical pathway includes the following key components during hospitalization: and an order within 24 hours of being admitted of a short acting bronchodilator, an antibiotic, and a steroid, as well as a standardized discharge plan. A patient's journey through the clinical pathway, ends at discharge. The discharge checklist requires that patients:

- Be on a long acting bronchodilator for 24 hours
- Be on a short acting bronchodilator is scheduled no more frequently than 4 times daily for 24 hours
- Be off IV steroids for 24 hours prior to discharge
- Have a steroid prescription, or have completed a 5-day course while admitted
- Have an antibiotic prescribed or have completed a 5-day course while admitted
- Have a scheduled appointment with a care provider within 5 days of discharge
- Receive COPD education during discharge

This proposed evaluation is designed to guide CHS strategy and quality improvement for COPD by applying research methodology and data analytics to create valid outcomes. Ultimately, as CHS deploys resource intensive interventions like this, it is important for the system and its patients to know answers to questions such as: Does this process impact readmissions and utilization?

This research project is a pragmatic, randomized quality improvement evaluation which seeks to evaluate the effects of standardizing the use of a COPD clinical pathway across various participating facilities among patients with an acute exacerbation of COPD. The outcomes evaluation of this quality improvement intervention has been designed to integrate into the routine care and minimize frontline staff burden by deploying an evaluation that occurs in a real-world setting with no additional data collection outside of usual care.

4. SUBJECT AND SITE SELECTION

4.1 Accrual

A daily patient list will be generated through an automated process utilizing clinical and patient registration information. The list will indicate patients newly hospitalized (hospitalization within the preceding 24-hour period) with symptoms of suspected acute COPD exacerbation, at any of the eight facilities. The list contains inpatient and observation encounters. The patient list will identify patients at any of the eight facilities throughout the project, not just once the facility has implemented the standardized use of the COPD clinical pathway. For the purposes of this project, we are not enrolling towards a targeted patient accrual. We will enroll patients during a pre-determined data collection period, See Section 6.

4.2 Subjects

An acute exacerbation is defined as an encounter where one the following criteria are met within 24 hours of admission.

- The use of the COPD PowerPlan **or**
- A respiratory therapy navigator notification of COPD exacerbation **or**

- The use of the respiratory therapy department COPD bronchodilator protocol **or**
- A historical diagnosis of COPD **or**
 - A history of COPD in the admitting documentation **or**
 - A COPD diagnosis on the problem list **AND**
 - An order of systemic steroids (prednisone or methylprednisolone)

To identify appropriate records of available clinical data for baseline and historical data collection and analysis, we will provision using the following ICD10 code for COPD: J44.1

4.3 Participating Sites

As part of the research design and rollout of this project, randomization will occur at the site level. CORE has randomized the facility participation order in advance of project kickoff. Site enrollment will begin with two facilities, adding on 2 additional facilities on a rolling basis in 2 month intervals, until all 8 facilities are active in using the COPD pathway. Once added, sites will begin utilizing the COPD clinical pathway in their daily practice with the target patient population.

The following Carolinas Healthcare System sites will be randomized for participation in this project.

- Carolinas HealthCare System Cleveland
- Carolinas HealthCare System Kings Mountain
- Carolinas HealthCare System Lincoln
- Carolinas HealthCare System NorthEast
- Carolinas HealthCare System Pineville
- Carolinas HealthCare System Union
- Carolinas HealthCare System University
- Carolinas Medical Center

4.4 Inclusion\Exclusion Criteria

4.4.1 Inclusion Criteria

Because this is a site-wide intervention, all patients who have a COPD exacerbation, as determined by their clinical care provider will be subject to receiving components of the intervention. Patients will be included in the daily Gap List based on the following criteria:

- ≥ 40 years of age at time of admission
- Identified as having an acute exacerbation of COPD within 24 hours of admission

4.4.2 Exclusion Criteria

Subjects must not meet any of the following criteria:

- Death during the index encounter
- Not discharged by the end of the study

4.5 Evaluable Population

Patients included in the evaluable population for this project, will have their data inform the final outcomes assessment. For the purposes of this project, the evaluable population will include patients who meet the same age criteria and have a discharge diagnosis of acute exacerbation of COPD: J44.1

5. OVERALL DESIGN

5.1 Outcome Variables

5.1.1 Primary Outcome Variable

The primary outcome variable is 60-day post discharge utilization (ED, inpatient, and observation encounters).

5.1.2 Secondary Outcome Variable(s)

Secondary outcome variables of the evaluation include:

Examining the COPD clinical pathway's effect on additional patient outcomes, such as the

- i. CHS Quality, Comfort, and Care 30-day readmission rate. This is a readmission rate among patients with an inpatient readmission to the same CHS facility as the index encounter.
- j. The patient-centric 30-day readmission rate. This is a readmission rate among patients with an inpatient or observation readmission to any CHS facility.
- k. The patient-centric 30-day readmission rate where the primary diagnosis of the readmission is COPD.
- l. Length of stay
- m. Rate of follow-up visit within 5 days of discharge.
- n. Antibiotic order rate during admission
- o. Steroid order rate during admission
- p. Short acting bronchodilator order rate during admission

5.1.3 Additional assessments

The methodology for identification of COPD exacerbation within the first 24 hours of hospital admission will be compared to retrospective identification through billing codes.

As a sub-analysis, qualitative outcomes will be collected and measured with patients, providers, and leaders. These outcomes will be collected and evaluated, per a sub-study protocol addendum.

5.2 Trial Design

5.2.1 Justification for stepped wedge cluster randomized control trial

The primary aim is to assess the effectiveness of a structured multidisciplinary care plans (intervention), compared with standard care (control) on 60-day non-elective acute care utilization (ED visits, observation, and inpatient encounters). The COPD clinical pathway will be delivered at the level of hospital or cluster, thus minimizing contamination and the risk of selection bias, if subjects were randomized at the individual level¹². Therefore, the unit of randomization and

analysis for this study will be the cluster. Considering logistical constraints and design rigor, the intervention will be rolled out sequentially instead of at the same time. Moreover, substantial and differential cluster-effects may exist because of distinct volume and characteristics of patients in each hospital. Thus, the stepped wedge design is advantageous compared with other alternative designs.

5.2.2 Randomization and allocation

The stepped wedge design implies a baseline period, in which no clusters are exposed to the intervention¹². Then, at the chosen time interval of two months, two hospitals will be randomized to cross from the control to intervention (**Figure 1**). This process continues until all eight hospitals have crossed over to the intervention. The order of this cross over process will be randomized. We will use block randomization to assign two hospitals at a time to switch from the control to intervention using SAS Enterprise Guide version 6.1. Allocation will be communicated only to hospital senior leadership initially to prevent contamination. Others including providers at the hospital will learn of allocation in the month preceding roll-out. Patients in included hospitals will be blinded to the intervention or control period.

[figure not shown]
Figure 1. The stepped wedge study design

| | 1-Apr | 1-Jun | 1-Aug | 1-Oct | 1-Dec | |
|-----------|-------|-------|-------|-------|-------|-----------------------------|
| Cluster 1 | 0 | 1 | 1 | 1 | 1 | 0=control 1=intervention |
| Cluster 2 | 0 | 1 | 1 | 1 | 1 | |
| Cluster 3 | 0 | 0 | 1 | 1 | 1 | |
| Cluster 4 | 0 | 0 | 1 | 1 | 1 | |
| Cluster 5 | 0 | 0 | 0 | 1 | 1 | |
| Cluster 6 | 0 | 0 | 0 | 1 | 1 | |
| Cluster 7 | 0 | 0 | 0 | 0 | 1 | |
| Cluster 8 | 0 | 0 | 0 | 0 | 1 | |

5.2.3 Sample size analysis

Calculations of sample size were based on the primary endpoints of 60-day non-elective acute care utilization. With the assumption of detecting a change in rates of 60-day non-elective acute care utilization from 43% in the control period to 33% in the intervention period, 59 patients with COPD exacerbation per hospital per two months is needed to achieve a power of 0.80 (intra-class correlation coefficients (ICC)=0.05 and two-side $\alpha=0.05$. Holding other parameters constant, the larger ICC is, the higher the power we will obtain (**Figure 2**). With sample sizes per cluster per two months ranging from 30 to 158, our preliminary data shows that the coefficient of variation (CV) of sample size is approximately 0.5. To account for this varying cluster size, we inflated the number of patients by 25% resulting in an average of 74 patients per hospital per two months¹³, resulting in a total sample size of 2960 patients among the intervention group and 5920 patients overall inclusive of our control population. The power was calculated by using the PASS 15¹⁴.

Figure 2. Alternative Sample Size Estimation

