
| | |
|-----------------------------|--|
| | 
• Be off IV steroids for 24 hours prior to discharge• A steroid prescription, or have completed a 5-day course while admitted• An antibiotic prescribed or have completed a 5-day course while admitted• A scheduled appointment with a care provider within 5 days of discharge• Received COPD education during discharge |
| Statistical Analysis | Analyses is among patients identified as having an acute exacerbation of COPD based on final billed coding. Comparisons of patients hospitalized during the intervention and usual care periods will be made using generalized estimating equations to control for clustering within hospital and repeated measures within hospital. The primary outcome, 60-day utilization, will be compared between the two groups of patients using a logit link in the generalized estimating equations. Results will be presented with odds ratios and 95% confidence intervals. |
| Sample Size Analysis | 8 hospitals will be randomized to intervention in 2 facilities per 2 month increments. With the assumption of detecting a change in rates of 60-day non-elective acute care utilization from 43% in the control period to 33% in the intervention period, 59 patients with COPD exacerbation per hospital per two months is needed to achieve a power of 0.80 (intra-class correlation coefficients (ICC)=0.05 and two-side $\alpha=0.05$). To account for this varying cluster size, we inflated the number of patients by 25% resulting in an average of 74 patients per hospital per two months, resulting in a total sample size of 2960 patients among the intervention group. |

LIST OF ABBREVIATIONS

| | |
|------|---------------------------------------|
| AE | Adverse Event or Acute Exacerbation |
| CHS | Carolinas Healthcare System |
| COPD | Chronic Obstructive Pulmonary Disease |
| EHR | Electronic Health Record |
| ED | Emergency Department |
| PHI | Private Health Information |
| PI | Principal Investigator |
| qid | 4 times per day |

TABLE OF CONTENTS

| | |
|--|------------------------------|
| 1. OBJECTIVES | ERROR! BOOKMARK NOT DEFINED. |
| 1.1. Hypothesis | 10 |
| 1.2. Primary Objective | 10 |
| 1.3. Secondary Objectives | 10 |
| 2. BACKGROUND | 10 |
| 3. RATIONALE | 10 |
| 4. SUBJECT AND SITE SELECTION | 11 |
| 4.1. Accrual..... | 11 |
| 4.2. Subjects..... | 11 |
| 4.3. Participating Sites..... | 12 |
| 4.4. Inclusion/Exclusion Criteria | 12 |
| 4.5. Evaluable Population..... | 13 |

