5.2.5 Primary aim

The primary outcome for this study is 60-day non-elective acute care utilization. Characteristics of the hospitals and individuals will be summarized by levels of randomization steps, hospitals and individuals. The count, rates and 95% confidence intervals of 60-day non-elective acute care utilization in the -control period will be presented and compared with that in the -treatment period. The primary analysis will be conducted using generalized estimating equations with fixed effects for intervention, time (steps), and intervention multiply by the time, accounting for the cluster randomized trial design with a random cluster (hospitals) effect. We will estimate and report the intra class correlation coefficients for all outcome measures to assess assumptions for sample size analyses and for future investigations using similar designs and outcomes. The primary analyses will follow the intention to treat principle with an additional per protocol analysis including by using denominator in those who had pathway ordered as well as intervention periods when truly occurred. The secondary analyses will include within cluster comparisons of intervention and control periods (not adjusting for any confounding effect of time), as well as comparisons of a series of (unbalanced) quasi-parallel cluster trials between those enrolled and unenrolled clusters at each intervention enrollment period. The same analyses plan will also be applied to secondary outcomes.

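### The stated 0.80 power matches a random-intercept, normal-theory calculation; a robust-variance GEE on 8 hospitals does not deliver both two-sided 0.05 and that power

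*Combined protocol and SAP*

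**What the plan says.** Section 5.2.3 and the synopsis (Sample Size Analysis) plan to detect a change in 60-day utilization "from 43% in the control period to 33% in the intervention period", with "intra-class correlation coefficients (ICC)=0.05" and two-sided alpha 0.05. They conclude that "59 patients with COPD exacerbation per hospital per two months is needed to achieve a power of 0.80". Section 5.2.3 then raises 59 by 25% to an average of 74 because hospital volumes vary (CV about 0.5). The only stated source for the power is PASS 15; the procedure, model and critical value are not given.

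Section 5.2.5 describes the analysis: "The primary analysis will be conducted using generalized estimating equations with fixed effects for intervention, time (steps), and intervention multiply by the time". The same sentence continues: "accounting for the cluster randomized trial design with a random cluster (hospitals) effect". The synopsis (Statistical Analysis) also names a GEE, with a logit link, and mentions no random effect. Neither place gives a working correlation, a variance estimator, degrees of freedom or an adjustment for having only 8 clusters.

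**The concern.** A marginal GEE has no random effects. It handles clustering through a working correlation and, usually, a sandwich variance. A random-intercept logistic model is a different analysis. Two analysts following Section 5.2.5 could therefore fit different primary models.

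The larger issue is the test. A GEE is customarily reported with a sandwich variance, which is biased downwards with few clusters, and 8 is few. Uncorrected, the test rejects too often. Corrected, it has less power than a normal-theory calculation suggests. Either way, the pair of figures in Section 5.2.3 would not describe the trial. An inflated alpha risks a false claim of benefit that then guides system strategy, the purpose given in Section 3. An overstated power risks over-reading a null result.

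**Working it through.** **Inputs.** Rates 0.43 and 0.33, ICC 0.05, two-sided 0.05, m = 59 and 74 (5.2.3). There are 8 hospitals, two crossing per step, over 5 periods (Figure 1, 5.2.2).

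**Step 1: reproduce 59.** With a random hospital intercept, fixed period effects and one intervention effect (Hussey-Hughes):

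Var = I·s·(s + T·τ²) / [(I·U − W)·s + (U² + I·T·U − T·W − I·V)·τ²]

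- I = 8 and T = 5.
- U = 20 intervention cells.
- W = 0² + 2² + 4² + 6² + 8² = 120.
- V = 2 × (4² + 3² + 2² + 1²) = 60.
- I·U − W = 160 − 120 = 40.
- The τ² coefficient is 400 + 800 − 600 − 480 = 120.
- Total variance is 0.43 × 0.57 = 0.2451, so τ² = 0.05 × 0.2451 = 0.012255.
- s = 0.95 × 0.2451 / 59 = 0.0039465.

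Var = 8 × 0.0039465 × (0.0039465 + 0.061275) / (40 × 0.0039465 + 120 × 0.012255) = 0.002059 / 1.62846 = 0.0012645, so SE = 0.0356.

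Power = Φ(0.10/0.0356 − 1.96) = Φ(2.812 − 1.96) = 0.803. At m = 58 it is 0.796, so 59 is the first integer to reach 0.80. At m = 74 it is 0.88. Eight variance conventions were tried. Two give exactly 59; the others need 53 to 62.

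**Step 2: same signal, few-cluster reference.** Refer the same noncentrality to t on 8 − 2 = 6 df (critical value 2.447). Power is 0.65 at 59 (noncentrality 2.812) and 0.74 at 74 (3.138). It first reaches 0.80 at 86 per hospital-period.

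**Step 3: simulation.** Binomial data on the Figure 1 layout, with ICC about 0.05, a constant hospital effect and a single pathway effect, 2,000 to 8,000 trials per setting. Ranges span runs and links. Power at 74 is for equal hospital sizes.

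| Test | Type I error | Power at 59 | Power at 74 |
|---|---|---|---|
| GEE, uncorrected sandwich, z | 14–16% | 0.86–0.87 (not at 5%) | – |
| GEE, Kauermann-Carroll, t(6) | 4.6–5.3% | 0.65–0.68 | 0.74–0.76 |
| GEE, Fay-Graubard, t(6) | 4.9–5.4% | 0.66–0.69 | – |
| GEE, Mancl-DeRouen, t(6) | 2.5–2.9% | 0.53–0.56 | – |
| GEE, model-based exchangeable, z | 4.8–6.4% | 0.80–0.83 | 0.89 |
| Random-intercept logistic, z | 6.4–7% | 0.80–0.82 | 0.88 |
| Random-intercept logistic, t(27) | 5.3–5.4% | 0.78 | 0.87 |
| Permutation over crossover orders | 5.0–5.8% | 0.76 | 0.85 |

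The permutation test uses all 8!/(2!)⁴ = 2,520 orders. Every sandwich version calibrated to exactly 5% gives 0.65–0.70 at 59, so the loss does not come from one choice of correction. With hospital sizes varying as the plan expects, Kauermann-Carroll t(6) power at an average of 74 is about 0.71–0.75. Over ICC 0.01–0.10 it is 0.62–0.73 at 59 and 0.71–0.81 at 74.

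**Step 4: hospital effects that drift.** The documents give no cluster autocorrelation. At assumed values of 0.9 and 0.8, the model-based GEE z test has type I error of 8.5% and 11.6%. Kauermann-Carroll t(6) stays at about 5%, but its power at 59 falls to 0.56 and 0.48.

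**Step 5: the interaction.** All figures above omit the intervention-by-time term in Section 5.2.5. With a linear interaction, the Step 1 calculation at 59 gives power between 0.22 (effect at the first or last period) and 0.80 (middle period). Power therefore depends on a contrast that the plan does not name.

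**The case against.** The strongest reply is that GEE as such is not the problem. If hospital effects are constant over time, the exchangeable working correlation is correct and a model-based GEE is valid: it holds roughly 5% with power of about 0.82 at 59 and 0.89 at 74. This stands. A reader might infer that no GEE can deliver 0.80 at two-sided 0.05, but the documents do not support that, because they never say which variance will be used. The loss comes from robust variance with few clusters.

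A reader might also infer that choosing between GEE and a random intercept would itself often change the trial's verdict. Like for like (model-based GEE z against random-intercept z), the two disagree on significance in only 2–3% of simulated trials, with odds ratios of 0.653 and 0.643.

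Two further points stand. The basis of the 0.80 is inferred from an exact match, and a t reference with large df cannot be excluded under some variance conventions. Also, 59 is the figure before inflation: at the planned average of 74 the shortfall from 0.80 is about 0.04–0.09, against about 0.14 at 59.

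The reply does not remove the point. The plan does not specify a model-based variance, and that test's error rate depends on hospital effects not drifting. The 25% inflation is already spent on unequal volumes.

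**Conclusion.** The point holds for the robust-variance GEE, the customary reading of Section 5.2.5. For that test the stated alpha and power are not both true. Type I error is about 14–16% uncorrected; held at about 5%, power is about 0.66 at 59 and 0.71–0.76 at 74, the lower values applying with unequal hospital sizes. A model-based exchangeable GEE or a random-intercept model keeps about 0.80 at 59 and 0.87–0.89 at 74, conditional on constant hospital effects. The random effect attached to a GEE is a contradiction in any case.

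These figures assume ICC 0.05, the plan's rates, the Figure 1 layout, a single intervention effect and, except in Step 4, hospital effects constant over time. They do not show that the trial needs more patients, because valid tests with power above 0.80 at 74 exist under those assumptions. The plan should be changed, but the design is not defeated.

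**What to change.** - **Section 5.2.5 and the synopsis (Statistical Analysis):** name one primary model and remove the contradictory term. State the single intervention contrast that is the primary test, either by moving the intervention-by-time term to a secondary analysis or by defining the contrast with that term in the model.
- **Same places:** specify a test valid for 8 clusters. One option is a GEE with a stated working correlation, a bias-corrected sandwich and t on 6 df. A second is a random-intercept logistic model with a small-sample reference, stating its reliance on constant hospital effects. A third is a permutation test over the 2,520 crossover orders. Deleting the random effect alone is not enough, since an unspecified GEE could still be run uncorrected.
- **Section 5.2.3 and the synopsis (Sample Size Analysis):** restate power for that exact test and contrast, and name the model and critical value used. For a single-effect model, expect about 0.66 at 59 and 0.71–0.76 at 74 with the corrected robust GEE, about 0.78 and 0.87 with the random-intercept model and a small-sample reference, or about 0.76 and 0.85 with the permutation test. If the interaction stays in the primary model, these figures do not apply and power must be recomputed.

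The cost is protocol wording and one power recalculation, with no added patients. The downside is a less favourable stated power if the robust GEE is kept.

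### The 25% allowance for unequal hospital sizes (59 to 74) is a parallel-trial upper limit, not the allowance this stepped-wedge design needs; it is conservative under the plan's own power model

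*Combined protocol and SAP*

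**What the plan says.** Section 5.2.3 assumes a fall in 60-day utilization "from 43% in the control period to 33% in the intervention period", with "intra-class correlation coefficients (ICC)=0.05" and a two-sided 5% test. On that basis "59 patients with COPD exacerbation per hospital per two months is needed to achieve a power of 0.80". It then reports volumes of 30 to 158 per hospital per two months and says that "the coefficient of variation (CV) of sample size is approximately 0.5". To allow for this, "we inflated the number of patients by 25% resulting in an average of 74 patients per hospital per two months", citing a paper on variation in cluster size in cluster randomised trials. The synopsis repeats the 25% and the 74. The stated totals, 2960 for the intervention group and (in 5.2.3 only) 5920 overall, are built on 74. No power is given at 74.

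Three other places bear on the point. Figure 1 in 5.2.2 shows eight hospitals over five two-month periods, with two hospitals crossing at each step. Section 4.3 says that "CORE has randomized the facility participation order in advance of project kickoff". Section 4.1 says that enrolment runs over a fixed period and not to a patient target.

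**The concern.** The 59 comes from a stepped-wedge calculation, but the 25% comes from a different design. In a parallel cluster trial the comparison is between hospitals, and unequal sizes add to the between-hospital variance. As clusters grow, the penalty approaches 1 + CV squared, here 1.25. In a stepped wedge with hospital and period effects, most of the information on the intervention is within hospitals, so unequal sizes cost much less. Section 5.2.3 itself notes that power rises with the ICC in this design, the opposite of parallel-trial behaviour.

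In a stepped wedge the cost of unequal sizes also depends on which hospitals cross when, and a single CV cannot capture that. At stake is whether 74, the figure carried into the totals, means what a reader would take it to mean: the size needed once unequal volumes are allowed for. Section 5.2.5 plans to report ICCs to help future studies of similar design, so others may reuse this calculation.

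**Working it through.** **Inputs.** From 5.2.3: rates 0.43 and 0.33 (difference 0.10), ICC 0.05, two-sided alpha 0.05, sizes 30 to 158, CV about 0.5. From Figure 1: I = 8 hospitals and T = 5 periods. The individual hospital volumes and the drawn order are not in the documents.

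**1. Reproducing 59.** Use the standard cross-sectional stepped-wedge variance with fixed period effects and a random hospital intercept, and total variance 0.43 × 0.57 = 0.2451. Then the between-hospital variance is τ² = 0.05 × 0.2451 = 0.012255, and the variance of a hospital-period mean is σ² = 0.95 × 0.2451 / 59 = 0.003947.

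From Figure 1:
- U = 20 intervention cells
- W = 0² + 2² + 4² + 6² + 8² = 120
- V = 2 × (4² + 3² + 2² + 1²) = 60

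Var = Iσ²(σ² + Tτ²) / [(IU − W)σ² + (U² + ITU − TW − IV)τ²]

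= 8 × 0.003947 × 0.065222 / (40 × 0.003947 + 120 × 0.012255) = 0.001264.

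SE = 0.0356 and 0.10/SE = 2.812, so power = Φ(2.812 − 1.960) = 0.803. This is the smallest size that reaches 0.80, so the plan's figure is reproduced. With equal sizes of 74, power is 0.881.

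**2. Reproducing 74.** 59 × (1 + 0.5²) = 59 × 1.25 = 73.75, rounded to 74. Even for a parallel trial of this cluster size the ratio is lower: [1 + (1.25 × 59 − 1) × 0.05] / [1 + 58 × 0.05] = 4.64 / 3.90 = 1.19.

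**3. Unequal sizes in the plan's model.** The same model was fitted by generalised least squares with unequal sizes, over all 8!/(2!)⁴ = 2520 crossover orders. One assumed set is 30, 45, 55, 62, 70, 80, 95, 158 (CV about 0.5), rescaled to each mean. Other sets spanning 30 to 158 gave the ranges in the last column.

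| Quantity | This set | Sets tried |
|---|---|---|
| Variance penalty, average over orders | 1.036 | about 1.03 to 1.04 |
| Variance penalty, worst order | 1.13 | about 1.12 to 1.16 |
| Average power at mean 59 | 0.789 | about 0.79 |
| Average power at mean 61 | 0.802 | about 0.80 |
| Mean giving 0.80 for essentially any order | 66 to 67 | about 65 to 68 |
| Average power at mean 74 (range over orders) | 0.869 (0.840 to 0.884) | about 0.87 (0.83 to 0.88) |

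A true 25% loss would leave an effective size of 59 / 1.25 = 47.2 and power 0.714. No order in these sets fell that low at a mean of 59; the minimum was about 0.74 to 0.75.

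**4. Sensitivity of these figures.** If the CV of 0.5 applies to every hospital-period cell and not to hospitals, the loss is about 7%, the size needed is about 63, and power at 74 is about 0.86. Across four conventions for the outcome variance, the average size needed runs from 59 to 64.

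**5. What the model leaves out.** The 0.87 rests on a constant ICC, a normal test and a single intervention effect. Changing one assumption at a time, at 74:
- Equal sizes, t reference on 6 to 7 df: power 0.74 to 0.77.
- CV 0.5, correlation decaying by an assumed factor of 0.8 per period: 0.59 to 0.61.
- Equal sizes, adding a linear form of the intervention-by-time term planned in 5.2.5: power for the intervention coefficient is 0.88 with time centred at mid-study, 0.57 one step away, and 0.26 at the first or last period.

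**The case against.** The strongest reply is that nothing goes wrong in practice. The multiplication is correct, the allowance is cautious and carries a citation, and 74 exceeds 0.80 power in the plan's model for every order examined. Enrolment is by calendar period, so no patient, estimate or test is affected. All of that stands, and it limits the weight of the point.

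A reader might infer three stronger things that the documents do not support.

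- *That the protocol misstates the power at 74.* It attaches 0.80 to 59 and gives no power at 74.
- *That 74 is about 20% too high.* 74/62 = 1.19 and 74/61 = 1.21, but 61 to 62 reaches 0.80 only on average. Depending on the assumed sizes, about 19 to 42% of orders fall below 0.80 there. Against a size safe for essentially any order, the excess is about 9 to 14% (74/68 = 1.09, 74/65 = 1.14).
- *That the trial has patients to spare.* The planned analysis has an intervention-by-time term and only eight hospitals, neither of which the power model reflects. The last step of the working shows that the apparent margin can vanish.

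What the reply does not rescue is the derivation. The 25% is presented as the allowance for unequal sizes in this design, and it is not. A margin with the wrong justification does not tell the reader what it protects against.

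**Conclusion.** The point holds in limited form. The 25% is a large-cluster upper limit for a parallel cluster trial. In the plan's own stepped-wedge model the allowance needed is about 3 to 4% on average and about 12 to 16% for the worst order, and the error is conservative there. These figures assume hospital sizes spanning 30 to 158 with CV about 0.5, because the actual volumes are not given. They also depend on the variance convention that returns 59. They describe the plan's power model and are not the power of the planned analysis. This is a wrongly derived planning figure worth restating. It is not an arithmetic slip, and it does not threaten the trial.

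**What to change.** In 5.2.3 and the synopsis, replace the 25% factor with stepped-wedge power computed from the eight hospitals' actual two-month volumes in the order already drawn, and state the power at the expected average of 74. Compute it under the analysis planned in 5.2.5, including the intervention-by-time term with its time coding stated. Use a small-sample reference suited to eight hospitals, and show a sensitivity range for correlation that decays over time. Do not just replace 74 with 61, and do not print 0.87 as the trial's power. If the 25% is kept as a margin, say that it is a conservative allowance taken from parallel trials.

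When the average is carried into the totals, use the 40 hospital-periods of Figure 1, 20 control and 20 intervention. At 74 that is 74 × 40 = 2960 for the whole trial and 74 × 20 = 1480 per condition. The text instead labels 2960 as the intervention group and gives 5920 overall.

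The cost is one recalculation from data the sponsor holds and a few sentences in two places. Enrolment does not change.
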